9.5 Data Analyses

The analytic approach in the second parallel trial is based on the minimum observed frequency of agitated and aggressive behaviors after intended exposure to the intervention (treatment) or after 8-months (control), conditional upon survival to at least one post-intervention observation (up to 4 months after baseline measurement). Our primary analysis is based upon an intent-to-treat principle, and we estimate complier average causal effect as a secondary analysis. The compliers analysis estimates the effects of the intervention for residents who received the music or would have received the music.

Our primary ITT analysis model is based on the model described by Murray & Blistein (2003) and Teerenstra et al (2012). Let Y_{ijk} be the staff interview for resident $i \in \{1, ..., n\}$ from NH $j \in \{1, ..., J\}$ at time $k \in \{baseline, post - exposure\}$, I_{ij} be an indicator that is equal to 1 if resident i in facility j is in the treatment group and T_{ij} is an indicator that is equal to 1 if this is the baseline score for resident i in facility j. We assume that $Y_{ijk} = \mu_{ijk} + \epsilon_{ijk}$, where $\epsilon_{ijk} \sim N(0, \sigma_{\epsilon}^2)$, and $\mu_{ijk} = \mu + \gamma T_{ij}I_{ij} + \tau(1 - T_{ij})(1 - I_{ij}) + \alpha(1 - T_{ij})I_{ij} + u_j + (u\tau)_{j,k} + s_{ij}$. We define $u_j \sim N(0, \sigma_u^2)$ as the deviation of cluster j from the overall mean, $(u\tau)_{j,k} \sim N(0, \sigma_{u\tau}^2)$ represent the variation of each cluster at different time points, $s_{ij} \sim N(0, \sigma_s^2)$ is the variation of individuals, γ is the difference at baseline between the mean of the intervention and control clusters, τ is the change from baseline to follow-up of the control clusters means, and α is the conditional treatment effect. Individual level covariates comprise of baseline variables including baseline CMAI. The estimate of interest would be the difference in marginal means.

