To estimate the effects among participants that would comply with the intervention we used a technique described by Jo et al. Let c_{ij} be an indicator that is equal to 1 if resident *i* in NH *j* would use the music if provided. We assume that residents who would not be offered the music will not attempt to obtain it on their own. Eligible residents who do not receive the intervention who and receive care in an intervention NH are referred to as "non-compliers." The effects of the intervention would be estimated using, $\mu_{ij} = \beta_0 + \beta_c c_{ij} + \alpha_c c_{ij} I_{ij} + \sum_{l=1}^{L} \gamma_{ijl} X_{ijl} + u_{nbj}(1 - c_{ij}) + u_{nwij}(1 - c_{ij}) + u_{cwij}c_{ij} + u_{cbj}c_{ij}$, where the macro-unit residuals u_{nbj} (non-compliers) and u_{cbj} (compliers) represent cluster-specific effects given I_{ijk} and X_{ijl} , which are assumed to be normally distributed with zero mean and the between-cluster variances σ^2_{nb} (non-compliers) are assumed to be normally distributed with zero mean and the within-cluster variance σ^2_{nw} (non-compliers) are assumed to be normally distributed with zero mean and the within-cluster variance σ^2_{nw} (non-compliers) are assumed to be normally distributed with zero mean and the within-cluster variance σ^2_{nw} (non-compliers) are assumed to be normally distributed with zero mean and the within-cluster variance σ^2_{nw} (non-compliers) are assumed to be normally distributed with zero mean and the within-cluster variance σ^2_{nw} (non-compliers) are assumed to be normally distributed with zero mean and the within-cluster variance σ^2_{nw} (non-compliers) are assumed to be normally distributed with zero mean and the within-cluster variance σ^2_{nw} (non-compliers) and σ^2_{cw} (compliers), and are equal across clusters. The following model for compliance status was assumed:

$$P(C_{ij} = 1) = \frac{exp\left(\sum_{l=1}^{L} \pi_{ijl}X_{ijl} + \tau_j\right)}{1 + exp\left(\sum_{l=1}^{L} \pi_{ijl}X_{ijl} + \tau_j\right)}$$

Where π_{ijl} are unknown parameters and $\tau_j \sim N(0, \sigma_\tau^2)$ so that the proportion of compliers may vary across clusters. Compliance status is only known in the intervention arm. Thus, a mixture model for compliance status in the control arm would be applied. Using the full likelihood, parameter estimates of the effect among compliers are estimated

$$\hat{\delta} = \left(\hat{\delta}_1 - \hat{\delta}_0\right) / \rho_c$$

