where $\hat{\delta}_t$ are the average CMAI among compliers in treatment group t and where ρ_c is the proportion of compliers. $\hat{\delta}_t$ can be obtained from the above models across NHs. The variance of this estimate can be obtained via the delta method or using Markov chain Monte Carlo techniques.

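### The complier effect divides a difference already taken among compliers by the proportion of compliers, so as written it is inflated by 1/ρ_c

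*Combined protocol and SAP*

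**What the plan says.** Section 9.5 (Data Analyses) makes intention to treat the primary analysis and the complier average causal effect a secondary one. It describes the target in these words: "The compliers analysis estimates the effects of the intervention for residents who received the music or would have received the music". The Précis gives the reason: the investigators also want to know the effect in residents who actually use the music.

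The model has a latent indicator c_ij, equal to 1 if the resident would use the music when it is provided. Assignment enters only through the product α_c·c_ij·I_ij, so non-compliers have no treatment term. Compliance is seen only in the intervention arm. For the control arm the plan says: "Thus, a mixture model for compliance status in the control arm would be applied".

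The estimator follows: "Using the full likelihood, parameter estimates of the effect among compliers are estimated", with δ̂ = (δ̂_1 − δ̂_0)/ρ_c. Its parts are defined directly below the formula. The δ̂_t "are the average CMAI among compliers in treatment group t", they "can be obtained from the above models across NHs", and the divisor is explained as "where ρ_c is the proportion of compliers". The variance is to come from the delta method or from Markov chain Monte Carlo.

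**The concern.** There are two usual routes to a complier effect. One compares all residents by assigned arm and divides by the proportion of compliers, because non-compliers dilute the difference. The other uses a mixture model to separate compliers from non-compliers in both arms and compares the compliers directly; there is then no dilution left to undo. Section 9.5 takes the numerator of the second route and the divisor of the first.

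The error always moves the estimate away from zero, and it grows as uptake falls. The plan allows for incomplete uptake. It lets the proportion of compliers vary between nursing homes (Section 9.5), raises recruitment in case some facilities fail to implement the program (Section 4.3.2), and changes delivery between the two trials (Section 5.1), partly to raise adherence (Précis). If uptake differs between the trials, so does the inflation, and the trial with poorer uptake would show the larger complier effect even if the true effect were the same in both.

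**Working it through.** **Inputs, all from Section 9.5**

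- Estimator: δ̂ = (δ̂_1 − δ̂_0)/ρ_c.
- δ̂_t: mean CMAI among compliers in arm t, taken from the fitted model.
- ρ_c: proportion of compliers. No value is given, so 0.4 to 1.0 is assumed below.
- Treatment term: α_c·c_ij·I_ij only.

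**The plan's own figures.** The documents state no complier effect and no ρ_c, so there is no figure on this point to reproduce. The related figure is the 24 nursing homes per arm in Section 9.2, and it does reproduce. With σ = 20, δ = 6, ICC = 0.12, r = 0.5, 15 residents per home, two-sided alpha 0.05 and 80% power:

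2 × (1.960 + 0.842)² × 400/36 × (1 + 14 × 0.12) × (1 − 0.25) = 350.6 residents

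350.6/15 = 23.4, rounded up to 24. The present point does not depend on this figure.

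**Step 1: what the numerator is.** For compliers (c = 1), the model mean differs between arms only by α_c. The random effects have mean zero, and the covariate terms cancel when both arm means are taken over the same complier population. Hence δ_1 − δ_0 = α_c.

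**Step 2: what the all-resident difference is.** Randomization gives both arms the same expected ρ_c, and non-compliers have no treatment effect:

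ITT = ρ_c × α_c + (1 − ρ_c) × 0 = ρ_c·α_c

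so ITT/ρ_c = α_c. This is the setting in which the division belongs.

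**Step 3: the formula as written.**

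(δ_1 − δ_0)/ρ_c = α_c/ρ_c = ITT/ρ_c²

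**Step 4: size, for a true complier effect of −6 points.**

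| ρ_c (assumed) | ITT = ρ_c·α_c | ITT/ρ_c | δ_1 − δ_0 | As written | Inflation |
|---|---|---|---|---|---|
| 1.0 | −6.00 | −6.00 | −6.00 | −6.00 | 1.00 |
| 0.9 | −5.40 | −6.00 | −6.00 | −6.67 | 1.11 |
| 0.8 | −4.80 | −6.00 | −6.00 | −7.50 | 1.25 |
| 0.7 | −4.20 | −6.00 | −6.00 | −8.57 | 1.43 |
| 0.6 | −3.60 | −6.00 | −6.00 | −10.00 | 1.67 |
| 0.5 | −3.00 | −6.00 | −6.00 | −12.00 | 2.00 |
| 0.4 | −2.40 | −6.00 | −6.00 | −15.00 | 2.50 |

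For a true complier effect of −4, the formula gives −4/0.8 = −5.0 at 80% compliers and −4/0.6 = −6.7 at 60%.

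**Step 5: simulation.** This used 2,000,000 residents per value of ρ_c, a true complier effect of −6, no effect in non-compliers, SD 20, no clustering (which does not alter the expected values), and compliance known in both arms.

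| ρ_c | ITT | ITT/ρ_c | Complier difference | As written |
|---|---|---|---|---|
| 0.8 | −4.79 | −5.99 | −5.98 | −7.48 |
| 0.5 | −2.97 | −5.94 | −5.99 | −11.97 |

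Both correct estimators return about −6. The formula as written does not.

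**Step 6: the standard error.** If ρ_c is treated as fixed, the estimate and its standard error are both multiplied by 1/ρ_c. The test against zero is unchanged, but both interval limits are stretched by that factor. If ρ_c is estimated, the delta method gives

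Var(α̂_c/ρ̂_c) ≈ Var(α̂_c)/ρ_c² + α_c²·Var(ρ̂_c)/ρ_c⁴ − 2·α_c·Cov(α̂_c, ρ̂_c)/ρ_c³

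which is the variance of a quantity that is not the complier effect.

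**The case against.** The strongest reply is that the harm is conditional. The section cites a published mixture technique and fits the full likelihood, and that fit yields α_c directly. An analyst who reports α_c reports the right number, and the closing formula does damage only if it is applied with its definitions taken literally. This is true, but the formula is the estimator that the plan prespecifies, so the plan is wrong as written.

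A second reply is that δ̂_t may have been meant differently. If it is the mean over all residents in arm t, the formula is the usual ITT/ρ_c. If it is the complier contribution averaged over all residents, E[c·Y_t], the difference is ρ_c·α_c and the division again gives α_c. Neither is what the definition says, nothing else in the documents redefines δ̂_t or ρ_c, and on either reading the definition would have to change.

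Several points on consequence stand:

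- The plan calls this a secondary analysis and does not rank it above other secondary analyses.
- The primary analysis and the sample size are untouched.
- With ρ_c fixed, the test against zero does not change.
- The 6-point figure in Section 9.2 is the planning difference for the primary outcome, so a complier estimate passing it has no formal meaning.
- Uptake may be high. Section 10.1 expects every observed resident to have received the music by the 8-month visit in the first trial. The inflation vanishes as ρ_c approaches 1.

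These limit the damage. They do not reconcile the formula with its definition.

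**Conclusion.** The concern holds. As written, the estimator equals α_c/ρ_c rather than α_c, and it overstates the complier effect by exactly 1/ρ_c whenever ρ_c is below 1. Over an assumed range of 90% down to 50% compliers the factor runs from 1.11 to 2.0; the true size cannot be fixed because the documents give no ρ_c. The result rests on the plan's own model (no treatment effect in non-compliers) and on its own definitions of δ̂_t and ρ_c. What suffers is the reported size of a secondary effect and its confidence limits. Because a prespecified estimator contradicts its own definition, this must be corrected before the analysis is run.

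**What to change.** In Section 9.5, choose one of two forms and state it without ambiguity:

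1. Keep δ̂_t as the mean among compliers and report δ̂ = δ̂_1 − δ̂_0, equivalently α̂_c from the mixture model, with no division. This fits the rest of the section best.
2. Keep the division and redefine δ̂_t as the mean CMAI over all residents in arm t, so that the numerator is the all-resident difference.

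Derive the delta-method or Markov chain Monte Carlo variance for the form chosen. Reporting the estimated ρ_c for each trial alongside the result would let readers check one against the other, since the all-resident difference divided by ρ_c should lie close to α̂_c.

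The cost is one line in the analysis plan. No data collection, design or sample-size change is needed.

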10 DATA COLLECTION AND QUALITY ASSURANCE

10.1 Onsite Data Collection (Trial 1 Only)

Procedures for onsite data collection are detailed in the *Manual of Procedures*. Briefly, on-site data collection will be used to capture primary study outcomes of frequency of agitated and aggressive behaviors, as well as secondary quality of life and engagement outcomes. Data collectors will also capture responses to music, collect metadata from iPods, and conduct an environment scan for observable characteristics of implementation. Data collectors will be flown to Providence, RI for a three-day intensify training for on-site data collection. During data collection months (baseline, 4-, and 8-months), Brown staff will have weekly phone calls with data collectors and supervisors. Visits will occur at baseline (pre-implementation), four months (mid-implementation), and eight months (full implementation). Each visit will be two days in duration. There are several activities to be completed before, during, and after the on-site data collection visits. The following is an overview of these activities.

Before Arrival: Site visit dates should be arranged approximately one month in advance of the visit by the project manager. In addition to the dates for the visit (2 consecutive days), the site should be made generally aware of the staff needed for the interview portion of the data collection. Approximately one week in advance of the on-site visit, the project director should reach out again to remind the NH of the upcoming site visit and request the facilities do the following in preparation:

- 1. Prepare a list of the people who are currently using the program, or, in the case of baseline and 4-month visits, are likely to use the music during the intervention.
- 2. Schedule time with nursing staff who are able to directly speak to the behaviors of these residents. The interviews take approximately 15 minutes per resident. If possible, these interviews should be scheduled for the first day of the site visit.
- 3. Ensure the person most familiar with the technology (iTunes, iPods) will be available during the visit. In this email, the project director should also ask the preferred time for the data collector to arrive and the person s/he should ask for upon arrival. This information needs to be communicated to the evaluator.

On-Site (Day 1): When the data collector arrives, she should first meet with the identified contact (often the administrator). The following tasks should be completed on the first day: 1) Obtain schedule for staff interview; 2) Interview staff at designated times; and 3) With assistance of staff, download metadata from personal music players.

The following information needs to be pre-populated in a secure tracking form to ensure the on-site data can be properly merged with the other administrative data used in this evaluation: resident last name, resident first name, birth month (MM), birth day (DD), birth year (YYYY), social security number (XXX-XX-XXXX), Point-Click-Care Enterprise ID (if available), and whether or not the resident has been exposed to the intervention (Y/N). The tracking form will have unique study identifiers. These unique identifiers cannot be traced to specific individuals without the tracking form, and will be used to link the staff interviews and direct observations to other administrative data integral to the study evaluation.

The data collector will interview NH staff members identified by the administration as being most familiar with the agitated and/or aggressive behaviors of the residents we will be observing during the second day of the visit. The purpose of interviewing the staff is to help us understand the frequency of behaviors. The staff member will be asked to approximate frequencies of specific resident behaviors over the past week and

estimate the amount of time staff spend attending to these behaviors. We will also ask staff to respond to items asking about the quality of life for this resident.

At the four- and eight-month site visits, the evaluator will assist staff in downloading the iPod metadata. iPod metadata refers to the information captured in iTunes when an iPod is synced via the designated M&M computer. Specifically, we are interested in capturing the following for each resident's playlist: song titles, song genres, song length, number of times a song has been played, and last time each song was played. By capturing the song length and the number of times a song has been played, we can better understand the amount of time the resident has received the intervention (approximate dose). By capturing last time the player was used, we can monitor attrition.

Off-Site (Day 1): All on-site data collection is completed assuming internet at NHs is not available or reliable. In the evening, between the first and second days, the data collector needs to: upload completed staff interviews in Qualtrics, and upload metadata to server.

On-Site (Day 2): The second day is dedicated to systematic observation of the residents, while using and not using the music. When the data collector returns the second day, she should notify the administrator or contact person that she is on-site and asked to be introduced to the nursing staff on the unit(s) where the observations will take place. Each of the residents will be observed at least 4 times during the day.

During the baseline visit none of the residents will have received the intervention. All observations will be of residents without the iPods. At the 8 month visit, all of the residents should have received the intervention and observations will be of residents while using and not using the iPods. At least four observations will be conducted for each resident: one in the morning; one mid-day; one in the late afternoon; and one with music (if music is being used for resident, else at a time chosen by data collector). At least one of the observations has to be during a meal. Residents will not be observed during any activities in which personal modesty is compromised (e.g., dressing or bathing). Whenever possible, residents will be observed in common areas, but may also be observed in their rooms with the door open or ajar. The evaluator should stand at an inconspicuous distance from the resident (minimum 5 feet from resident).

Off-Site (Day 2): All on-site data collection is completed assuming internet at NHs is not available or reliable. In the evening, after the second day, the data collector needs to: upload completed observations in Qualtrics and complete the implementation observation. The implementation observation captures direct observations of how the equipment is being stored and used by staff, and gestalt impressions of staff familiarity and buy-in. The implementation observation will be completed by the evaluator immediately after leaving the site on the second day.

All other data are derived from existing data. Please see Section 6 which details these sources.

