Eligible facilities will have at least 15 long-stay residents with moderate to severe dementia, defined as a diagnosis of dementia and either a Brief Interview for Mental Status score \leq 12 or moderately or severely daily decision-making. Preliminary research and pilot data informs our estimates of the potential effect of M&M on any improvement in agitated and aggressive behaviors. Assuming an intra-class correlation (ICC) of 0.12 and 6 points reduction in the outcome variable of interest (staff reporting of resident agitated and/or aggressive behaviors), we need 24 NHs in each arm to be able to test our primary outcome with power of .8 with a two-tailed alpha of .05. Since we plan on recruiting 27 facilities per arm, we will have adequate power even if we encounter unforeseen circumstances.

STUDY TEAM ROSTER

Principal Investigator:

[name] Professor of Health Services, Policy & Practice Florence Pirce Grant University [name] for Gerontology and Healthcare Research Brown University, School of Public Health Providence, RI 02912 [contact] [contact]

Co-Investigators:

[name] Assistant [name] for Gerontology and Healthcare Research Health Services, Policy & Practice Brown University, School of Public Health [name] [contact] [contact] Role: project director, co-Investigator

[name] Associate Professor of Biostatistics Brown University, School of Public Health [name] [contact] [contact] role: co-Investigator, statistical design and analysis lead

[name] Associate Director, Center for Long-Term Care Quality & Innovation Associate Professor of Practice, Department of Health Services, Policy & Practice Center for Gerontology and Health Care Research Brown University, School of Public Health Providence, RI 02912 [contact] [contact] Role: co-Investigator, intervention committee lead, corporate liaison, supervises consultants

[name] Director of the Center of Innovation in Long Term Services and Supports (LTSS COIN) Associate Professor of Medicine Associate Professor of Health Services, Policy and Practice Brown University & Providence VA Medical Center [contact] Role: co-Investigator, implementation science lead

[name], MA Associate Professor of Health Services, Policy and Practice

Protocol, Version 3.0

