9.2 Sample Size and Randomization

The primary outcome for this study is agitated and aggressive behaviors, as measured by the Cohen-Mansfield Agitation Inventory (CMAI). We have three ways of measuring agitation and aggression – the Minimum Data Set (MDS), the Cohen-Mansfield Agitation Inventory (CMAI), and the direct observation of residents while using and not using the music. Prior research suggests that agitated behaviors are underascertained in the MDS, due to staff normalizing these behaviors when exhibited by the residents.(86) For this reason, we chose the CMAI as our primary study outcome. We based our sample size estimates and analytic plan on the CMAI (staff interview).

Sample size estimates are based on the primary trial outcome: total score on the CMAI among long-stay residents with dementia. Based on data from the first trial, We conducted a *post hoc* power calculation to estimate the required sample size for different effect sizes. We used the formula proposed by Teerenstra et al (2012) and imputed values from the trial data. For significance level α and power 1- β , the formula for the required number of residents is:

$$n_{res} = \frac{2\left(Z_{1-\frac{\alpha}{2}} + Z_{1-\beta}\right)^2 \sigma^2}{\delta^2} (1 + (n-1)\rho)(1-r^2),$$

where Z_x is the critical value from a normal distribution at x, σ^2 is the variance of the outcome CMAI, δ is the effect size, ρ is the intra-class correlation, n is the number of residents per cluster and r is the correlation between a cluster means at baseline and at follow-up. To obtain the number of clusters required per arm we would need n_{res}/n . In our parallel design experiment completed just before the pandemic, we found that $\sigma = 20$, $\rho = 0.12$ and r = 0.5. Assuming an alpha level of 0.05 and power of 80%, we need 24 NHs per study arm to detect a 6-point reduction in the total CMAI score. We recruited 27 NHs per study arm which will allow us to address possibly higher ICC values, non-participation and lower correlation between the baseline and outcome scores.

9.2.2. Treatment Assignment Procedures: Please refer to section 4 for a detailed description of the treatment assignment procedures.

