11 PARTICIPANT RIGHTS AND CONFIDENTIALITY

11.1 Institutional Review Board (IRB) Review

The METRICAL protocol was reviewed and approved by the Brown University Institutional Review Board (IRB).

Informed Consent Forms

The Brown IRB approved two waivers of individual consent. The Brown Institutional Review Board (IRB) approved a waiver of informed consent for secondary data under 45 CFR 46.116. This waiver covered the obtainment and linkages of EHR, MDS, Medicare Enrollment and Vital Status Data, and iPod metadata. The Brown IRB also approved a waiver of informed consent for the proposed primary data collection under 45 CFR 46.116. This made it possible to collect primary data for all eligible residents, and to link staff interview and direct observation data to the available secondary data.

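### Section 10.1 ties the 8-month CMAI list in Trial 1 intervention homes to current music use, which conflicts with the intent-to-treat comparison and must be reconciled

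*Combined protocol and SAP*

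**What the plan says.** Section 10.1, headed as applying to Trial 1 only, sets out what a home prepares about a week before each visit. Item 1 is to "Prepare a list of the people who are currently using the program". For the baseline and 4-month visits only, the item also admits residents who are likely to use the music. Item 2 is to "Schedule time with nursing staff who are able to directly speak to the behaviors of these residents". The Day 1 text says the interviews concern the residents to be observed on Day 2. The Day 2 text adds: "At the 8 month visit, all of the residents should have received the intervention". No separate instruction is given for control homes.

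On the analysis side:

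- Section 9.5 states: "Our primary analysis is based upon an intent-to-treat principle".
- The précis (Design and Outcomes) compares the last observed total agitation score among residents who meet the eligibility criteria, in treated and control groups, and covers both study years.
- The complier model in section 9.5 defines non-compliers as eligible residents of intervention homes who do not receive the music.

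On the consent waiver for primary data, section 11.1 says: "This made it possible to collect primary data for all eligible residents".

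**The concern.** Music use at 8 months is a post-randomization variable. If it decides who has an 8-month CMAI, intervention-home residents who were never offered music, declined it or stopped are left out at that visit. No corresponding filter can operate in control homes. The 8-month comparison then sets users in one arm against some other, undefined group in the other.

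Section 4.3.3 already warns that homes with many eligible residents can be selective about who gets the program, so users and non-users may well differ in agitation. The complier analysis would also lack 8-month outcomes on the non-compliers whose distribution it has to model.

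**Working it through.** **The plan's own figure.** Inputs: two-sided alpha 0.05 and power 0.80 (précis, Sample Size and Population: "with power of .8 with a two-tailed alpha of .05"); effect 6 points, SD 20, ICC 0.12 and r = 0.5 (section 9.2); 15 residents per home (Table 1: 405/27 = 15).

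- Residents per arm = 2 × (1.960 + 0.842)² × 20²/6² × (1 + 14 × 0.12) × (1 − 0.5²) = 2 × 7.849 × 11.11 × 2.68 × 0.75 = 350.6.
- Homes per arm = 350.6/15 = 23.4, rounded up to 24.

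This agrees with "we need 24 NHs per study arm to detect a 6-point reduction in the total CMAI score". The sample size is not in question.

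**Standard error of the contrast** with 27 homes of 15 per arm: √(2 × 400 × 2.68 × 0.75/405) = 1.99 points.

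**Form of the bias.** Let c be the share of intervention-home residents who are measured, and g the mean CMAI of non-users minus that of users, after adjustment for baseline. The full-cohort mean is c × (users) + (1 − c) × (non-users). Measuring users alone therefore shifts the intervention mean by (1 − c) × g. If non-users are more agitated, the shift favours music. If homes keep music for the more agitated residents, it works against music.

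**Illustration.** The documents give neither c nor g, so all values below are assumptions. The gap is either 5 points (0.25 SD) with none of it explained by baseline, or 2.5 points if baseline explains half. Type I error is Φ(b/SE − 1.96) + Φ(−b/SE − 1.96), with b the bias and SE = 1.99.

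| c | g (points) | Bias (points) | Two-sided type I error |
|---|---|---|---|
| 0.7 | 2.5 | 0.3 × 2.5 = 0.75 | 6.6% |
| 0.5 | 2.5 | 0.5 × 2.5 = 1.25 | 9.6% |
| 0.7 | 5 | 0.3 × 5 = 1.5 | 11.7% |
| 0.5 | 5 | 0.5 × 5 = 2.5 | 24.1% |

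The last two rows are upper illustrations, because they combine a baseline-adjusted SE with an unadjusted gap. All four rows assume that an unmeasured resident contributes no follow-up score at all. With c = 0.9 and g = 2 the bias is only 0.1 × 2 = 0.2 points.

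**Loss of numbers is minor.** With only users measured in the intervention arm, SE = √(300 × [(1 + (15c − 1) × 0.12)/(27 × 15c) + 2.68/405]). This is 2.06 at c = 0.7 and 2.15 at c = 0.5. Power for 6 points is then 82.9% and 79.7%, against 85.3% with everyone measured. The issue is bias, not precision.

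**Is there an overriding list rule elsewhere?**

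- Section 6.1 says the CMAI assesses eligible residents, but not how they are listed at each visit.
- The tracking form (section 10.1, Day 1) has a yes/no exposure field, and the Day 2 observation rule has an alternative for residents not using music. Both allow for non-users. Neither requires that 8-month non-users be listed.
- Section 11.1 says what the waiver made possible.
- Section 13 has a committee give intervention homes lists of eligible residents, without saying that the CMAI follows those lists.

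None of these replaces item 1 at 8 months.

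**The case against.** A reader might infer that the primary outcome was collected only on compliers, so that the intent-to-treat analysis cannot be delivered. The documents do not support that, for four reasons.

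- The exposure field, the Day 2 alternative and the complier model all presuppose that some non-users are in the data. Item 1 is a scheduling request in a self-described overview that defers to a Manual of Procedures not available here. Applied literally, it would give every control home an empty 8-month list, so it was probably not meant as a cohort definition.
- Current users are not the documents' compliers. Section 9.5 counts residents who received the music, or would have, so someone who used it and stopped is still a complier.
- CMAI data are also collected at 4 months, when likely users are listed. The last observed score (précis) or the minimum (section 9.5) can use that value.
- Section 10.1 covers Trial 1 only, and section 9.2 describes that trial as completed. Section 9.5 introduces its approach for the second trial. Nothing carries item 1 into Trial 2.

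All of this stands and limits the point. Two things remain. First, the 4-month score is a partial rescue: a resident who had rejected music by then is neither a current nor a likely user and can be missed at both visits. For those who stop later, the last score comes from month 4 while controls can contribute month 8. Second, the précis promises the eligible-resident comparison for both years, so the conflict does not depend on section 9.5 alone.

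**Conclusion.** The point holds as a contradiction within the protocol. The written 8-month list in Trial 1 intervention homes depends on post-randomization use, has no workable control-home counterpart, and works against the intent-to-treat, eligible-resident and complier analyses. No other section states a rule that overrides it. For Trial 2, where primary data are again collected, no CMAI listing rule is stated. The request in section 5.1 for 15 eligible residents' preferred genre and age is a playlist step.

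The size is illustrative only: 0.75 to 2.5 points against the 6-point target, in an unknown direction, resting on an assumed 50% to 70% of residents measured and an assumed adjusted gap of 2.5 to 5 points. It shrinks as more non-users contribute a 4-month or 8-month score. What was done in the field cannot be judged from these documents.

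**What to change.** **Trial 2.** State one rule in the protocol and the Manual of Procedures: residents listed at baseline are followed at every visit in both arms while alive and in the home, whether or not they use music.

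**Trial 1.** Collection is complete, so the remedy lies in the analysis:

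- define the intent-to-treat set as the baseline-listed residents;
- exclude from the primary analysis users added to the list later;
- report missing 4-month and 8-month CMAI by arm and use status;
- add a supporting analysis of the MDS Aggressive Behavior Score in all MDS-eligible residents of both arms, which needs no staff-made list.

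The baseline list is itself chosen by staff as likely users. A fixed cohort removes selection after baseline but not that first choice, which is why the MDS analysis is worth having. If the Manual of Procedures already holds a different rule, move it into the protocol.

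**Cost.** One sentence, about 15 minutes of interview per visit for each listed non-user in Trial 2, and a small amount of extra analysis of data the study already receives.
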